Opioid use in rural areas has reached epidemic proportions in the United States.^[1-3] Outbreaks of HIV and HCV have been associated with syringe sharing among partners injecting prescription opioids in rural Indiana, and increases in heroin and fentanyl-related drug overdose deaths have been reported throughout the Midwest.^[2, 4, 5] Illinois ranked as the third highest state in percentage increase in death rates involving synthetic opiates between 2014-2015.^[3] Rural areas in southern Illinois may be disproportionately affected by the epidemic. The southernmost 16 counties in Illinois are part of the federally designated Delta Regional Authority (Illinois Delta Region; IDR), an area of 252 counties and parishes described as the most economically distressed area of the country.^[6] These areas have been adversely affected by loss of coal mining and agricultural employment, population decline, and defunding of public services, and they are both geographically proximate to and share many of the demographic characteristics as Scott County, IN. Public health surveillance data indicate that some Illinois counties in this largely rural and poor area have seen tremendous increases in opioid use, overdose, and HCV and STD transmission. However, the epidemiological factors underlying this increase, including demographic factors, sociocultural influences, healthcare access, and community resources are largely unknown. Our previous work in rural communities has demonstrated substantial variation in a number of these factors.^[7]

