- Assistance with the hiring of study staff who will be located at the community organizations to conduct consenting, interviews and survey administration.
- Assistance with study equipment purchasing, such as iPads, in instances where they have access to lower pricing
- Provide space for consenting, interviewing or survey administration if needed.

[name],

[name] will serve as a consultant on this project. Additionally, he will provide training to study staff, and will participate in the interviewing of study subjects.

Community Action Place, Inc. (CAP)

CAP will be engaged in research. They will recruit from their clients who participate in syringe services as well as HIV/HCV testing services.

[name], Director, Institute for Infectious Disease Research – New York University
[name] will conduct analysis on identified study data.

[name], Postdoctoral Fellow, – New York University
[name] will conduct analysis on identified study data.

[name], MPH, Assistant Professor - Cornell University
[name] will support qualitative analysis development, instrument guide development and analysis and will participate in the interviewing of study subjects.

[name], CHES – Austin Peay State University
[name] will adapt the survey and qualitative instruments and lead in the analysis pertaining to the sexual and gender minority population in ETHIC on de-identified data only. She will lead on conference abstract and manuscript development.

8) Data analysis

Data analysis will be performed by Drs. [name], [name], [name], Friedman, [name] and [name] as well as [name]. Additional statistical analysis will be performed by members of the Biostatistics Laboratory at the University of Chicago.

- a) Descriptive statistics, network characteristics and disease burden analyses:
Demographic, drug use characteristics, sexual risk behaviors, psychosocial measures and HIV, HCV, HBV and STD status will be analyzed using standard descriptive and comparative statistical analyses. Specifically, t-tests and Chi-square analyses will compare groups for continuous and categorical variables; logistic regression will examine factors associated with disease presence; and repeated measures ANOVA assess factors associated with re-infection/treatment failure. Statistical significance will be assumed with p-values <0.05.

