- b) Qualitative analysis: Interviews will be analyzed using an inductive thematic approach. At the conclusion of each interview, the interviewer will develop a broad free-text memo detailing any prevailing observations or interpretations from the interview. These interview memos will then be reviewed and discussed with another member of the research team.

An open coding protocol and thematic analysis will be carried out using ATLAS TI (v. 8.0).^[18] This process will be prefaced by the development of a set of *a priori* codes, generated through a close reading of the transcripts, interview memos and relevant peer-reviewed literature, to produce an initial codebook. Each transcript will be coded by one coder; for additional fidelity, a second coder will code a subset of transcripts.

Discrepancies will be resolved through discussion. Emergent themes will be identified the transcripts and memos, following inductive thematic analytic techniques.

- c) Epidemiological analysis of public health datasets: We will perform descriptive analysis as described in section as well as use multilevel Poisson regression models to select indicators associated with resident zip codes for patients with emergency department (ED) visits related to heroin and nonmedical prescription drug use in Illinois. This outcome measure is captured by the State syndromic surveillance system. Potential indicators will be selected from a range of datasets including PMP, EMS, treatment and arrest data. ED visits will be modeled against each indicator and in a multilevel Poisson regression model with counties as random effects and total emergency department visits as the offset. We will use backwards stepwise regression to select indicators significantly associated with ED visits.

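### The zip-code model of drug-related ED visits is Poisson with only a county random effect, so if zip codes vary within counties, significance-based selection keeps too many chance indicators

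*Protocol*

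**What the plan says.** Protocol section 8) c), on the epidemiological analysis of public health datasets, sets out a regression "to select indicators associated with resident zip codes for patients with emergency department (ED) visits" related to heroin and nonmedical prescription drug use. The unit of analysis is therefore the zip code.

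- **Model:** a "multilevel Poisson regression model with counties as random effects and total emergency department visits as the offset". County is the only random effect named.
- **Candidates:** "Potential indicators will be selected from a range of datasets including PMP, EMS, treatment and arrest data". Their number is not given.
- **Selection:** "We will use backwards stepwise regression to select indicators significantly associated with ED visits".
- **Significance level:** none is given in 8) c). Section 8) a) says "Statistical significance will be assumed with p-values <0.05".

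Neither document mentions overdispersion, a negative binomial or quasi-Poisson alternative, a zip-level random effect or robust standard errors. There is also no validation or multiplicity step for the selection. The SAP covers the RE-AIM outcomes and does not mention this model.

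**The concern.** A Poisson model sets the variance equal to the mean, given the terms in the model. Here those terms are the measured indicators and a county intercept. Two zip codes in the same county are therefore assumed to differ only through the indicators and Poisson noise. Any other zip-level difference is extra variance that the model does not count, and the standard errors of indicators that vary between zip codes within a county come out too small.

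In this analysis the p-value is itself the selection rule, so understated standard errors directly lengthen the list of retained indicators. That list is part of the epidemiological work for UG3 Aim 1, which seeks the areas at greatest risk. Aim 3 then applies that work to service expansion.

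The protocol gives reason to expect some zip-level variation. It plans zip-level mapping of drug-related ED visits, and its background says the factors behind the regional increase are largely unknown. It gives no estimate of the variation.

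**Working it through.** The plan states no sample size, power or dispersion figure for this model, so there is no figure of its own to reproduce.

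**Inputs from the documents.** The unit is the zip code, county is the only random effect, and selection is backward on significance. Alpha is 0.05, borrowed from section 8) a) and taken as two-sided. The region has 16 counties (Protocol background: "The southernmost 16 counties in Illinois are part of the federally designated Delta Regional Authority"). Section 8) c) refers to Illinois as a whole, so the data may be statewide; 16 counties is used as the regional case.

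**Assumed inputs.** 5 or 8 zip codes per county; mean drug-related visits per zip code (mu) of 2, 10 or 30; within-county SD of the log rate (tau) from 0 to 0.5; county SD 0.3; 10 candidate indicators with no true association.

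**Step 1: formula.** If the true variance is phi times the mean and the model takes phi = 1, then

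- model SE / true SE = 1/sqrt(phi)
- true size of the test = 2 × P(Z > 1.96/sqrt(phi))

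For phi = 2: 1.96/1.414 = 1.386, size 16.6%. For phi = 3: 1.96/1.732 = 1.132, size 25.8%. For phi = 5: 1.96/2.236 = 0.877, size 38.1%.

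**Step 2: from zip-level variation to phi.** With log-normal variation between zip codes, phi = 1 + mu × (exp(tau²) − 1).

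| mu | tau | phi | size by formula |
|---|---|---|---|
| 2 | 0.3 | 1 + 2 × 0.0942 = 1.19 | 7.2% |
| 10 | 0.2 | 1 + 10 × 0.0408 = 1.41 | 9.9% |
| 10 | 0.3 | 1 + 10 × 0.0942 = 1.94 | 16.0% |
| 10 | 0.5 | 1 + 10 × 0.2840 = 3.84 | 31.7% |
| 30 | 0.3 | 1 + 30 × 0.0942 = 3.83 | 31.6% |

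**Step 3: simulation of the planned model.** Poisson with a county random intercept, backward elimination at p < 0.05, 300 replicates per row. The same model was also fitted as negative binomial (NB). The false-positive rate is per noise indicator in the full model.

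| Zips per county | mu | tau | Poisson: model SE / empirical SD | Poisson: false positives | Poisson: noise kept of 10 | NB: false positives | NB: noise kept of 10 |
|---|---|---|---|---|---|---|---|
| 8 | 10 | 0 | 1.03 | 5.3% | 0.54 | 5.0% | 0.49 |
| 8 | 2 | 0.3 | 0.92 | 9.5% | 0.93 | 7.8% | 0.68 |
| 8 | 10 | 0.2 | 0.85 | 11.5% | 1.21 | 7.0% | 0.62 |
| 5 | 10 | 0.3 | 0.75 | 16.6% | 1.82 | 8.4% | 0.70 |
| 8 | 10 | 0.3 | 0.70 | 19.3% | 2.10 | 7.7% | 0.70 |
| 8 | 10 | 0.5 | 0.49 | 36.3% | 3.76 | 7.1% | 0.66 |
| 8 | 30 | 0.3 | 0.48 | 37.9% | 3.80 | 7.3% | 0.70 |

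The simulated rates run a few points above the formula but follow the same order. Where zip-level variation is present, the chance of keeping at least one noise indicator is 62% to 99% with Poisson and 43% to 49% with negative binomial. With no such variation it is 41% with Poisson and 38% with negative binomial.

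**The case against.** The strongest reply is that the size of the problem rests on quantities the documents do not give: the number of zip codes, events per zip code, number of candidates and within-county variance. Rural zip codes may have low counts, and at 2 events per zip code the inflation is modest (9.5%). With no residual zip-level variation the planned model holds its level. This stands, and it is why the point is conditional and the size is a range.

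Second, not every indicator is affected. Protocol section 3) c) allows prescription-monitoring measures at zip code or county level. For a county-level indicator, the county random effect already carries most of the relevant variance. This also stands.

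Third, backward elimination keeps about 0.5 of 10 noise indicators even when the standard errors are right. Only the excess is due to the Poisson assumption.

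A reader might infer three stronger things that the documents do not support:

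- **That the high-risk areas themselves would be misplaced.** Section 8) d) locates hot spots with LISA and Gi* statistics, not with these p-values. The epidemiological analysis is meant to inform that work, so any effect on it is indirect.
- **That the trial's reported outcomes are at risk.** The SAP's RE-AIM outcomes do not use this model.
- **That the offset is wrong because it is given as visits and not log visits.** In a log-link model that wording is ordinary shorthand for the exposure, and nothing in the section points to an unlogged offset.

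**Conclusion.** The point holds in conditional form. The planned model has no term for variation between zip codes within a county, and its p-values decide which indicators are kept. If such variation exists beyond the measured indicators, standard errors for indicators that vary within a county are too small and the list contains too many chance associations.

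Under the assumed inputs above, a nominal 5% test rejects about 10% to 38% of the time and 0.9 to 3.8 of 10 noise indicators are kept, against about 5% and 0.5 with no zip-level variation. Apart from alpha and the 16 counties, every numerical input to that range is an assumption.

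The consequence is limited to which indicators an exploratory Aim 1 analysis reports as associated with drug-related ED visits. The change is still worth making, because the error is foreseeable and cheap to prevent.

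**What to change.** In Protocol section 8) c), replace the Poisson model with a negative binomial mixed model, or add a zip-level random effect to the Poisson model. Keep the county random effects and total ED visits as the exposure. Base the backward selection on that model's p-values, and report the estimated dispersion so that readers can see how much it mattered.

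The cost is one changed model statement, and the public health datasets can be refitted. The downside is larger standard errors and fewer indicators retained. If dispersion proves negligible, the results will barely change.

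The change does not cure stepwise selection. With zip-level variation present, the negative binomial version still rejected 7.0% to 8.4% of noise indicators and kept 0.62 to 0.70 of 10, so the resulting list should be reported as exploratory.

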Additional analysis will be performed using de-identified, aggregate data from the Illinois Prescription Monitoring Program (PMP) under a Data Use Agreement between the University of Chicago and the Illinois Department of Human Services. This analysis will include zip code level data on opioid prescribing, including total morphine milligram equivalents (MMEs), buprenorphine prescribing and high-risk practices (benzodiazepine – opioid co-prescribing, multiple prescribers / pharmacies) at the zip code or county level. No patient or prescriber identifying information will be analyzed.

Publicly available data from the Illinois Youth Survey (<https://iys.cprd.illinois.edu/>), the SAMHSA Buprenorphine Treatment Locator (<https://www.samhsa.gov>) and the Illinois Criminal Justice Authority http://www.icja.state.il.us/research/overview#tab_research-data) will be analyzed to understand self-report opioid use among school age children, number of buprenorphine-waivered prescribers and drug index arrest data in the IDR.

d) GIS Mapping:

We will use geographic information system (GIS) methods to create zip code-level measures of accessibility scores for the following service types in the IDR: 1) local health department services (in aggregate and for each relevant service, including STD clinics, HIV testing, PReP clinics, needle exchange services, naloxone training sites, etc) 2) pharmacies and veterinary supply retail (i.e. locations where clean syringes can be purchased); 3) mental health services; 4) hospitals; 5) safety net clinics. This GIS method, the two step floating catchment area (2SFCA) method^[9], which will utilize data on geocoded addresses of services relative to the population who may need those services. We will utilize zip code tabulation area estimates of population who may utilize these services (e.g. those aged 15 and older). Zip code tabulation areas are generalized representation of U.S. zip codes developed by the U.S. Census Bureau. These population estimates will be obtained from the publicly available U.S. Census Bureau's American Community Survey.

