- d) GIS hot spot analysis for resource clustering: We will first produce choropleth maps of all spatial accessibility scores as well as zip code level aggregate data from the Illinois Department of Health and other state entities on infection rates (i.e. HIV, Hepatitis C, chlamydia, gonorrhea), ED visits related to heroin and nonmedical prescription drug use, opioid overdose deaths, criminal justice outcomes. We will perform zip code level hot spot analysis of accessibility scores. Hot spots are areas where the variable of interest (e.g. access to harm reduction, etc.) is significantly higher in magnitude than expected by random chance. We will calculate Local Indicators of Spatial Autocorrelation (LISA) statistics in ARCGIS to determine if the rates of the variables of interest are significantly geographically clustered. If significant clustering is identified, we will use the Getis-Ord tool in ARCGIS to calculate the Gi* statistic, which is used to identify clusters (i.e. census tract) of hot spots. We will also perform bivariate LISA to assess the relationship between accessibility scores and health outcomes (e.g infections, ED visits) to determine if there are areas of low accessibility to services and high levels of PWUD-related outcomes, for example. Both forms of LISA statistics can help determine areas that may be geographic targets for intervention.
- e) PWUD Characterization and Exploration of Social Network: This prospective analysis will apply and adapt the extensive expertise of the study team in ethnographic and survey research, network analysis, and non-probability sampling among PWUD (Friedman, [name], [name]) to an otherwise unstudied population in the IDR. In the first stage, an ethnographic approach will use interviews to inform the development of a survey instrument. Study participants will be recruited using Respondent Driven Sampling (RDS) and a matching will be performed to estimate the social network characteristics of PWUD including injecting and sexual behaviors. Ethnographic and survey data will be used to inform SSP service expansion, outreach, and targeted telehealth programs. Longitudinal analysis will be performed to evaluate acceptability of interventions.
- n) Social Network Estimation: An augmented social network will be generated based upon existing matching protocols^[19, 20] that generate ties between respondent's self-reported

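### LISA and Gi* significance on two-step floating catchment access scores can reflect overlapping catchments instead of clustered services, by an amount set by a catchment size the protocol does not state

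*Protocol*

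**What the plan says.** Protocol section 3 d) (GIS Mapping) plans to "create zip code-level measures of accessibility scores for the following service types in the IDR", using "the two step floating catchment area (2SFCA) method" with geocoded service addresses and census population estimates.

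Protocol section 8 d) takes those scores as the variable to be tested: "We will perform zip code level hot spot analysis of accessibility scores". A hot spot is an area where the variable is "significantly higher in magnitude than expected by random chance". The steps are:

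- LISA statistics "to determine if the rates of the variables of interest are significantly geographically clustered".
- A conditional second stage: "If significant clustering is identified, we will use the Getis-Ord tool in ARCGIS to calculate the Gi* statistic".
- A joint analysis: "We will also perform bivariate LISA to assess the relationship between accessibility scores and health outcomes".

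The section adds that both forms of LISA may help to pick target areas for intervention. It also plans choropleth maps of all the access scores before any testing.

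Neither section states a catchment distance or travel time, spatial weights, the number of zip codes or sites, a reference distribution for random chance, or a multiplicity rule. A significance level appears only in section 8 a): "Statistical significance will be assumed with p-values <0.05". The SAP does not cover the GIS work.

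**The concern.** The usual reference for LISA and Gi* is a map on which the observed values are dealt out at random over the zip codes. A two-step floating catchment score is a moving sum over sites within a radius. Two nearby zip codes whose catchments overlap include many of the same sites with the same supply ratios, so their scores are alike however the sites came to be located. The exchangeable-values null is then false because of how the score is built, and rejecting it does not show that services cluster more than chance would produce.

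At stake is the meaning of the word significant on the access maps. A label that depends heavily on an unstated radius would be reported as a statistical finding. It would decide whether Gi* is run and could support the choice of areas for expanded services.

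**Working it through.** The protocol gives no error rate for this analysis, so there is no figure to reproduce. The check asks how often the planned tests call access clustered when services are placed at random.

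**Inputs.** From the protocol: the score, the zip code unit, LISA then Gi*, and bivariate LISA. Taken from section 8 a) by assumption: alpha 0.05. Assumed because not stated: zip code centroids and sites uniform and independent in an 80 x 80 mile square, lognormal zip code populations, 6 nearest neighbours as weights, and catchments of 2 to 30 miles.

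**Score.** Step 1, for site j: R_j = 1 / (population within radius r of site j). Step 2, for zip code i: A_i = sum of R_j over sites within r of zip code i.

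**Why neighbours agree.** For two circles of radius r with centres d apart, put u = d/(2r). The shared area fraction is (2/π)[arccos(u) − u√(1 − u²)], and zero if u ≥ 1. With 120 zip codes, typical spacing is d = √(6400/120) = 7.3 miles.

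| r (miles) | u | shared fraction |
|---|---|---|
| 2 | 1.83 | 0 |
| 5 | 0.73 | 0.16 |
| 10 | 0.37 | 0.55 |
| 20 | 0.18 | 0.77 |
| 30 | 0.12 | 0.85 |

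So at 10 miles adjacent zip codes share about half their catchment, and at 20 miles about three quarters.

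**Local and global Moran, services at random** (80-120 zip codes, 15-40 sites):

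| r (miles) | zip codes flagged by local Moran | maps rejected by global Moran |
|---|---|---|
| 5 | 6-7% | 11-29% |
| 10 | 13-19% | 73-98% |
| 20-30 | 33-42% | 100% |

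Nominal is 5% in both columns. Section 8 d) names LISA, not global Moran, and does not say what LISA result counts as significant clustering. The global column is therefore only one map-level reading of the gate.

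**Gi*** (120 zip codes, 10 or 40 sites). Without correction it flags about 7% of zip codes at 2 miles, 7-8% at 5, 12-15% at 10, 38-39% at 20 and 44-46% at 30. The same scores shuffled over zip codes give 5-7%. Control of the false discovery rate does not remove the effect: at 20-30 miles 27-36% of zip codes stay flagged, and every map has at least one, against 6-7% of shuffled maps.

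**Is the null the cause?** Keep the score, but draw the reference maps by relocating the sites at random and recomputing A_i (120 zip codes). Global Moran rejection:

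| r (miles), sites | shuffled-score null | relocated-site null |
|---|---|---|
| 5, 10 | 35% | 3.7% |
| 10, 10 | 97% | 5.7% |
| 20, 10 | 100% | 6.0% |
| 20, 40 | 100% | 4.0% |
| 30, 40 | 100% | 6.3% |

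Zip codes flagged hot at one-sided 0.05 are 5.0-5.7% under relocation, against 5.7% (5 miles) rising to 26.9% (30 miles) under shuffling. Changing only the null restores the error rate.

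**Bivariate test.** Pairing the access score with a spatially independent outcome gives rejection of 1-10%, close to nominal. Pairing it with an outcome that is unrelated to access but spatially smooth (assumed 15-mile range) gives 29-58%. The inflation needs spatial correlation in both variables.

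**The case against.** Several points on the other side are sound.

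- **No catchment is stated.** A reader might infer that such a score can never meet the null, or that the gate to Gi* must always open. The documents do not support that. At 2 miles global rejection is about 9-11%, and at 5 miles local flagging is barely above nominal. Wide catchments are plausible in a rural 16-county region, but that is an assumption.
- **The scores are real data.** A reader might infer that a significant access cluster says nothing beyond the chosen radius. That is also too strong. The scores come from actual service addresses and population estimates, and neighbouring zip codes that share a clinic do share access. High and low areas are valid descriptions, and the planned choropleth maps already show them.
- **Bivariate LISA.** A reader might infer that the access score alone spoils it. Against a spatially independent outcome it does not. Spatially correlated outcomes are plausible here, but the problem is then the general one of two autocorrelated variables, not a fault special to the catchment method.
- **Limited consequence.** The targeting language is tentative, Aim 1 also draws on surveillance, utilisation, prescribing and arrest data, and no RE-AIM outcome in the SAP depends on these maps.

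These points narrow the concern but do not remove it. The protocol defines a hot spot by comparison with random chance and makes significance the condition for Gi*. For a catchment-smoothed score, the standard tests do not make that comparison correctly once catchments span several zip codes.

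**Conclusion.** The concern holds in a limited form. The significance labels that LISA and Gi* attach to floating catchment scores, and the significance gate between them, are unreliable when catchments cover several zip codes. Under the assumed layouts the excess in local Moran is negligible at 5 miles, roughly three to four times nominal at 10 miles (13-19% against 5%), and roughly seven to eight times nominal at 20-30 miles (33-42% against 5%). These figures rest on a square region, uniform random sites, 6 neighbours and alpha 0.05. None of these is fixed by section 8 d), so the range matters more than any single value.

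Tests on infection, emergency department and overdose rates are not affected by this mechanism, because those rates are not catchment-smoothed. Bivariate p-values are too small only where the outcome is spatially correlated as well.

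**What to change.** In sections 3 d) and 8 d):

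1. State the catchment size and the spatial weights.
2. Report access scores by quantile or against a stated threshold, without LISA or Gi* p-values. If a test is wanted, use a Monte Carlo null that relocates the service sites and recomputes the score each time, and define random chance accordingly.
3. Keep LISA and Gi* for observed outcome rates.
4. For access against outcome, report a descriptive cross-classification of low-access by high-outcome zip codes, or use a null that preserves the spatial correlation of both variables.

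The cost is wording and re-run maps, with no new data. The access maps lose a simple ArcGIS p-value, and the relocation null needs some extra computation.
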